Hysterosalpingo-contrast sonography (HyCoSy) was introduced as a safer and less-painful alternative to HSG with comparable diagnostic accuracy and superiority in diagnosing uterine, ovarian, and myometrial pathologies.(1,6,9,10-12) HyCoSy is the recommended tubal test by NICE for women not known to have tubal disease, as an alternative to HSG, whenever appropriate expertise is available.(3) Air and saline use as contrast medium with HyCoSy made the procedure highly operator dependent.(1,6,13-16) Hyperechogenic and longer-lasting echogenic media then followed but are currently commercially unavailable or not approved for tubal testing.(1,6,14– 19)

In 2007, ExEm gel (GynaecologIQ, Delft, Netherlands) was introduced(20) and registered as European Confirmatory (CE) approved drug for tubal testing.(15) Hysterosalpingo-foam sonography (HyFoSy), using diluted ExEm gel foam, has been established as a safe, feasible, tolerable, and accurate alternative to HyCoSy and HSG that has been widely used in infertility clinics.(1,6,7,9,10,14,18,19,21–26)

In 2017, hysterosalpingo-lidocaine-foam sonography combined with power doppler (HyLiFoSy-PD) was introduced as a cost effective and less painful possible alternative to HyFoSy that can be used whenever the contrast media is unavailable. "Flaming tube" sign, detected using power doppler (PD), was also described as to allow easier recognition of tubal patency.(27) Our study aims to compare the diagnostic accuracy of HyLiFoSy-PD with the most commonly used tubal test; HSG, with reference to the gold standard tubal test; laparoscopy and dye testing.

5. Objective:

The aim of this study is to evaluate the difference between the diagnostic accuracy of Hysterosalpingo-lidocaine-foam sonography and hysterosalpingography, with reference to the gold standard tubal test; laparoscopy with dye testing.

6. Study Design:

This will be a cross-sectional study

7. Scientific committee approval:

8. Study methodology:

Population of study, disease condition and setting:

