Women in the reproductive age group between 18- and 40-years old presenting with primary or secondary infertility who underwent HSG in the previous 5 years as a part of their infertility work-up with availability of good-quality HSG images, & did not get pregnant in this period, and gave no history of incidences that might affect their tubes, such as : abdominal surgery or laparoscopy, pelvic inflammatory disease, smoking, and intrauterine device insertion.

Women fitting these inclusion criteria and scheduled for LDT as part of their infertility work up will be considered. HyLiFoSy-PD will be carried out few days before the already scheduled LDT.

The study will be conducted in the Cairo fetal medicine unit, department of Obstetrics and gynecology, Cairo university.

Inclusion criteria:

- 1. Age group (18-40)
- 2. Informed signed Written consent.
- 3. Scheduled for LDT as a part of their infertility management

- 4. Have undergone HSG in the previous 5 years with the availability of good-quality HSG images.
- 5. No incident factors that might have affected the tubal status after she underwent HSG within the previous 5 years, such as ; abdominal surgery or laparoscopy, pelvic inflammatory disease, smoking, and intrauterine device insertion.

Exclusion criteria:

Women with any of these factors will be excluded:

- 1. LDT scheduled for a therapeutic purpose due to a known tubal or ovarian pathology
- 2. Lack of good-quality HSG images.
- 3. Withdrawal of consent.
- 4. Using contraception
- 5. Women outside reproductive age
- 6. Known allergy to lidocaine
- 7. Active pelvic inflammatory disease
- 8. Undiagnosed genital tract bleeding.
- 9. Evident tubal pathology (such as hydrosalpinx) or pregnancy diagnosed by transvaginal ultrasound (TV-US) prior to performing HyLiFoSy-PD

Methodology in details

Interpretation of HSG results:

Review of the HSG films will be done for assessment of the tubal patency; tubes will be considered patent if the dye is seen throughout their whole length and till their ends with a positive immediate spill or a spill in the delayed film. If the dye does not pass through one or both cornual ends, or if a part of the tube is seen filled with dye but not the whole length then tubal obstruction will be considered. Patients with hydrosalpinx seen by HSG are to be assessed first by US if no visible hydrosalpinx is seen by US and she has no signs of PID then she can proceed to the HyLiFoSy-PD procedure.

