- 12.Patients will be asked about the degree of discomfort or pain they felt during and immediately after the procedure. Using categorical verbal rating scale (VRS),(28) Procedure will be stopped if a patient experiences severe pain.
- 13.Patients will be followed up overnight and monitored for any other procedure-related side effects or complications.
- 14. Within a week following the HyLiFoSy-PD procedure, standard LDT will be carried out by experienced endoscopists who will be blinded to the results of HyLiFoSy-PD. During LDT, tubal patency will be tested using methylene blue dye. Tubal evaluation during LDT will be classified as: patent with immediate spill, patent with delayed spill, or blocked.

Possible Risk (mention if there is any risk or not)

Side effects such as vasovagal reactions, allergic reaction, and venous intravasation have been reported in literature in hysterosalpingo-foam studies. However, in our previous hysterosalpingo-lidocaine-foam sonography study, none of these side effects were encountered. For the possible risk of infection, all patients will be given prophylactic antibiotics. In addition, any case with visible hydrosalpinx or signs or symptoms of PID on US prior to performing HyLiFoSy-PD will not perform the procedure.

9. Study outcomes:

Primary outcomes

1. Diagnostic accuracy of HyLiFoSy and HSG with reference to LDT, in terms of sensitivity, specificity, positive predictive value, negative predictive value, and overall accuracy.

Secondary outcome parameters

1 -Diagnostic accuracy of adding power doppler to the HyLiFoSy.

2-Evaluate the procedure associated pain

3-Evaluate the procedure duration

4-Percentage of failed or inconclusive attempts and possible reasons for

that

5-Incidence and rate of potential complications for example: vasovagal and allergic reactions, venous intravasation.

10. Sample size: Using the following equation:(29)

$$N_{\text{Disease}} = \frac{\left\{z_{1-\alpha/2}\Lambda + z_{1-\beta}\sqrt{\Lambda^2 - \zeta^2(3+\Lambda)/4}\right\}^2}{\Lambda\zeta^2}$$

where $\Lambda = (1 - Se_1)Se_2 + (1 - Se_2)Se_1$ and $\zeta = (1 - Se_1)Se_2 - (1 - Se_2)Se_1$.

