With power of the study 90%, CI 95%, average sensitivity of HSG is 0.55,(4) and sensitivity of HyLiFoSy-PD is 90%,(30), prevalence of tubal pathology is 30%,(1); 100 patients are required to fulfill the sample size. To compensate for any possible dropouts (5%), 5 more patients will be recruited. So, the total sample size will be 105.

11. Statistical analysis:

After recording and collecting the data, statistical analysis will be performed using the Statistical Package for the Social Sciences (SPSS, version 16.0, SPSS Inc, Chicago, Illinois, USA). Data will be statistically described in terms of mean and standard deviation if they were of normal distribution, and in terms of median and range if they were not normally distributed. Frequencies (number of cases) and percentages will be used when appropriate. Accuracy will be represented using the terms sensitivity, specificity, PPV, NPV, and overall accuracy. Testing the difference in the results of tests was done using

one-way analysis of variance (ANOVA) test. P-values less than 0.05 will be considered statistically significant.

12. Source of funding:

Self-funding

13.Time plan From 1/6/2022 – 1/6/2024 (2 years)

14.References:

- Optimal evaluation of the infertile female. Fertility and Sterility. 2006 Nov;86(5 SUPPL.).
- Fertility problems: assessment and treatment Clinical guideline [Internet]. 2013. Available from: www.nice.org.uk/guidance/cg156
- 5. Tsiami A, Chaimani A, Mavridis D, Siskou M, Assimakopoulos E, Sotiriadis A. Surgical treatment for hydrosalpinx prior to in-vitro

KASR ALAINY

Cairo University

fertilization embryo transfer: a network meta-analysis. Ultrasound Obstet Gynecol. 2016 Oct 1;48(4):434–45.

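### The only significance test in section 11 is a one-way ANOVA on an undefined quantity, although HSG and HyLiFoSy give paired patent/blocked readings and section 10 sizes a paired comparison of sensitivity

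*Combined protocol and SAP*

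**What the plan says.** Section 11 first describes accuracy: "Accuracy will be represented using the terms sensitivity, specificity, PPV, NPV, and overall accuracy". The next sentence gives the only comparison method: "Testing the difference in the results of tests was done using" a "one-way analysis of variance (ANOVA) test. P-values less than 0.05 will be considered statistically significant". No other test is named anywhere. There is no confidence interval for a difference in accuracy, and no statement of whether the unit is the tube or the woman.

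The rest of the plan describes a paired comparison.

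- **Objective (section 5):** to "evaluate the difference between the diagnostic accuracy of Hysterosalpingo-lidocaine-foam sonography and hysterosalpingography", with LDT as the reference.
- **Design (section 8):** each woman must "Have undergone HSG in the previous 5 years with the availability of good-quality HSG images", and "HyLiFoSy-PD will be carried out few days before the already scheduled LDT". One woman therefore contributes both index tests and the reference.
- **Scale (section 8):** HSG and greyscale HyLiFoSy are each read as patent or occluded. LDT is classed as "patent with immediate spill, patent with delayed spill, or blocked".
- **Sizing (section 10):** the formula gives a number of diseased subjects from the expected discordance Λ and the difference ζ between two sensitivities. Its inputs are "average sensitivity of HSG is 0.55,(4) and sensitivity of HyLiFoSy-PD is 90%,(30), prevalence of tubal pathology is 30"%, with 90% power and a 95% confidence level.

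**The concern.** One-way ANOVA is built for a continuous outcome in independent groups. Here the outcome is binary and the two tests are read in the same women, so the named test does not match the design or the sample-size calculation.

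The plan also leaves open what is analysed. At least three readings are possible:

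1. the raw blocked/patent results, with test as the group factor;
2. correct/incorrect calls against LDT in all women;
3. correct/incorrect calls in LDT-blocked women only.

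Only the third is the comparison that section 10 sizes. The first does not compare accuracy at all: two tests can call the same share of women blocked while one is right far more often. Because the text does not choose, the choice could be made after the data are seen.

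**Working it through.** **Plan's own figure.** Inputs from section 10: Se₁ = 0.55, Se₂ = 0.90, two-sided 0.05, power 0.90, prevalence 0.30.

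- Λ = 0.45 × 0.90 + 0.10 × 0.55 = 0.46
- ζ = 0.45 × 0.90 − 0.10 × 0.55 = 0.35
- N_Disease = {1.960 × 0.46 + 1.282 × √(0.46² − 0.35² × 3.46/4)}² / (0.46 × 0.35²) = 30.83
- 30.83 / 0.30 = 102.8, so 103 women. The stated 100 corresponds to rounding down to 30 diseased (30 / 0.30).

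The same formula gives 89.0% power at 30 diseased and 90.2% at 31. The sizing is therefore a paired, McNemar-type comparison of sensitivities and does not rest on ANOVA.

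**What each reading of the ANOVA tests.** HSG specificity is 0.87 (section 4). HyLiFoSy specificity is not given, so 0.87, 0.95 and 1.00 are assumed. The expected proportions called blocked are:

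- HSG: 0.3 × 0.55 + 0.7 × 0.13 = 0.256
- HyLiFoSy: 0.3 × 0.90 + 0.7 × (1 − Sp) = 0.361, 0.305, 0.270

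At specificity 1.00 the positivity rates differ by 1.4 points, although sensitivity differs by 35 points and specificity by 13. ANOVA power by simulation follows (400,000 replicates per scenario, 100 women, tests conditionally independent given LDT status, LDT-blocked count binomial with mean 30 except in the last row):

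| What enters the ANOVA | Sp 0.87 | Sp 0.95 | Sp 1.00 |
|---|---|---|---|
| Raw results, HSG vs HyLiFoSy | 33.0% | 6.6% | 1.4% |
| Raw results, LDT as a third group | 17.3% | 3.1% | 1.4% |
| Correct/incorrect, all women | 51.0% | 92.3% | 99.7% |
| Correct/incorrect, 30 LDT-blocked women | 89.1% | 89.1% | 89.1% |

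On the first reading, power falls as the new test improves.

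**ANOVA against McNemar on correct/incorrect calls.** Dependence between the tests uses a bivariate-normal latent model; the correlation of 0.5 is an assumption.

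| Comparison | Independent: ANOVA / McNemar | Correlation 0.5: ANOVA / McNemar |
|---|---|---|
| Sensitivity 0.55 vs 0.90, 30 LDT-blocked | 89.1% / 87.0% | 92.2% / 95.2% |
| Specificity 0.87 vs 0.95, 70 LDT-patent | 39.2% / 35.8% | 37.5% / 43.9% |
| Overall accuracy, 100 women, HyLiFoSy Sp 0.87 | 51.0% / 50.3% | 51.1% / 61.4% |

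**Type I error of ANOVA in 30 LDT-blocked women**, at common sensitivity 0.55, 0.725 and 0.90: 5.1%, 5.0% and 5.4% under independence; 1.7%, 1.8% and 2.7% at correlation 0.5. Expressed by discordance, with both sensitivities at 0.725, it is 4.9% at 0.40 (close to independence), 0.6% at 0.20 and 0.03% at 0.10. Asymptotic McNemar gives 4.3%, 4.8% and 3.0%.

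**The case against.** The strongest reply is that the lowest powers come from a reading the plan's context argues against. Sections 5 and 9 both speak of accuracy relative to LDT, and the sentence just before the ANOVA one lists accuracy measures. Sensitivity and specificity would also be reported in any case, so a gain would be visible even if the test missed it.

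On the sized comparison, the section 10 formula itself takes the tests as conditionally independent, and under that assumption ANOVA loses nothing: 89.1% against 87.0%, with type I error near 5%. On 0/1 data in two groups it behaves almost like a two-proportion test, so the continuous-outcome assumption matters little. Where the tests are positively correlated, the error is on the conservative side and would not produce a false claim of superiority.

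Most of this stands, and it limits the harm. It does not rescue the sentence. Nothing in section 11 conditions on LDT status, and its literal wording refers to test results, not to correct calls. Nor can the ANOVA readily be assigned to a secondary outcome: pain is recorded on a categorical scale, and pain and procedure duration are described only for HyLiFoSy, so there are no groups to compare.

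Two neighbouring matters are not part of this point. Delayed spill at LDT is already patent by its category name. The gap between 100 and 103 women is rounding, and 105 are to be recruited, which gives 105 × 0.30 = 31.5 expected LDT-blocked women if none drops out.

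**Conclusion.** The concern holds, and the sentence must be corrected. The only test offered for the primary objective has no defined input, ignores the pairing and is not the test that was sized.

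The consequence ranges widely with the reading: power from about 1% to above 99% across plausible inputs. If the analysis is restricted to LDT-blocked women, the planned 35-point difference would rarely be lost. The cost there is a type I error below nominal and some loss of power for smaller differences, both arising only when the tests agree more than independence implies.

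The whole-sample figures rest on assumed HyLiFoSy specificities, and the correlated figures on an assumed latent correlation of 0.5. The mismatch between the named test, the design and the sizing rests on the documents alone.

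**What to change.** Replace the ANOVA sentence in section 11. Suggested wording, with the woman as the unit, as in the sizing:

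> The primary comparison is the sensitivity of HyLiFoSy versus HSG among LDT-blocked women, by McNemar's test (two-sided 0.05), with a paired 95% confidence interval for the difference. Specificity will be compared in the same way among LDT-patent women, and overall accuracy by McNemar's test on correct/incorrect calls in all women. PPV and NPV will be compared by a paired method such as GEE or a generalised score test.

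PPV and NPV need a separate method because their denominators differ between the two tests.

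Fix the unit before the data are seen. If it is the woman, define when she counts as LDT-blocked with only one tube blocked. If it is the tube, match readings by side and replace plain McNemar with a method that clusters by woman. Section 9 lists five accuracy measures without ranking them; putting sensitivity first follows section 10.

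The cost is wording only, with no new data items. State whether McNemar is asymptotic or exact, because this affects power. At exactly 30 LDT-blocked women and conditional independence, simulated power is 87% for the asymptotic version and 81% for the exact one. With the count left random around 30, it is 86% and 80%. The change does not by itself secure the stated 90%, and if the exact test is chosen the sample size should be rechecked.
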